9.3.4.5 Severity Assessment

Severity assessments are based on the intensity of the event in relation to expectation. The Investigator will assess the intensity of AEs based on the Common Terminology Criteria for Adverse Events (CTCAE), Version 5.0 grading system as follows¹:

- Grade 1: Mild; asymptomatic or mild symptoms, clinical or diagnostic observations only; intervention not indicated.
- Grade 2: Moderate; minimal, local or noninvasive intervention indicated; limiting age appropriate instrumental activities of daily living.
- Grade 3: Severe or medically significant but not immediately life-threatening; hospitalization or prolongation of hospitalization indicated; disabling; limiting self-care activities of daily living.
- Grade 4: Life-threatening consequences; urgent intervention indicated.
- Grade 5: Death related to AE.

¹ https://ctep.cancer.gov/protocolDevelopment/electronic_applications/docs/CTCAE_v5_Quick_Reference_8.5x11.pdf

Severity is a measure of intensity whereas seriousness is defined by the criteria outlined in [Section 9.3.4.4](#). An AE of severe intensity need not be considered serious. For example, nausea that persists for several hours may be considered severe nausea, but not meet serious criteria, and would, therefore, be assessed as a severe AE but not an SAE.

9.3.4.6 Causality Assessment

The investigator (or designee) will determine the causality of all AEs to the study drug using medical judgment and considering all relevant factors including, but not limited to, the underlying study indication, coexisting disease, concomitant medication, relevant history, pattern of the AE, temporal relationship to the study drug, and de-challenge or re-challenge information. The causality assessment of the AE/SAE is to be made as described below.

Related to study drug (possibly, probably, or definitely related)

Based on medical judgment, there is at least a reasonable possibility that the study drug caused the event; one or more of the following criteria apply:

- The event follows a reasonable temporal sequence from administration of study drug.
- The event could not be reasonably attributed to the known characteristics of the patient's clinical state, environmental or toxic factors, or other modes of therapy administered to the patient.
- The event follows a known pattern of response to study drug.
- The event disappears or decreases on cessation or reduction in dose of the study drug (positive de-challenge). It should be noted that, in some situations, an AE will not disappear or decrease in intensity upon discontinuation of study drug despite other clear indications of relatedness.
- The event reappears or worsens when the study drug is re-administered (positive re-challenge).

Unrelated to study drug (unlikely or unrelated)

Based on medical judgment there is no reasonable possibility that the study drug caused the event; one or more of the following criteria apply:

- The event does not follow a reasonable temporal sequence from administration of study drug.

- The event could be reasonably attributed to the known characteristics of the patient's clinical state, concurrent illness, environment or toxic factors, or other modes of therapy administered to the patient.
- The event does not follow a known pattern of response to study drug.
- The event does not disappear or decrease on cessation or reduction in dose of the study drug, and it does not reappear or worsen when the study drug is re-administered.

Default assessments of the related category without supportive evidence for a causal relationship to study drug is generally uninformative and does not contribute meaningfully to the development of the safety profile of the drug or to patient safety.

9.3.4.7 Recording of Adverse Events

Monitoring of AEs will be conducted throughout the study after patients sign the ICF. Adverse events will be collected for all patients, including screen failures, and recorded in the eCRF for all enrolled patients. It is the investigator's (or designee's) responsibility to assess the severity, seriousness, and causality to study drug for each AE and record it in the eCRF. All AEs and SAEs, regardless of attribution, should be reported until 14 days after the last administration of study treatment or until study discontinuation/termination, whichever occurs later. Patients will be assessed at the End of Study Visit to determine if any new AEs have occurred. After this period, investigators (or designees) should report only SAEs that are considered related to study drug.

Any AEs or SAEs that are unresolved at the patient's last AE assessment in the study are to be followed up by the investigator (or designee) until resolution or stabilization, up to database lock, and recorded in the eCRF. Albireo AB retains the right to request additional information for any patient with ongoing AEs or SAEs at the end of the study.

If there is a clinically significant deterioration of a laboratory value/vital sign or other routine study assessment that is associated with a diagnosis, the clinical diagnosis will be reported as an AE and the associated signs and symptoms will be considered additional information unless the sign or symptom is more severe than expected given the diagnosis. For example, if an investigator (or designee) diagnoses a study patient with hepatitis during the study period, hepatitis would be considered the AE and the concomitant signs and symptoms of abdominal pain, vomiting, and elevated ALT and AST would not be reported separately unless, in the opinion of the investigator (or designee), one of these signs or symptoms is more severe than expected and therefore a separate AE assessment is indicated.

9.3.4.8 Recording and Reporting of Serious Adverse Events

All SAEs, regardless of severity and causality, that occur from signing of the ICF through the last study visit or 14 days after the last dose of study drug, whichever is later, must be reported immediately and not later than within 24 hours of knowledge of the event by the investigator (or designee) on the SAE eCRF.

Serious AE reports must include at least the following information:

- Patient identification information (study number, site number, initials, and date of birth [as per local country requirements for data protection])
- The event term. Provide the diagnosis term, if known. If a diagnosis is unknown, provide the signs/symptoms and update the event term once a diagnosis is known
- The date of onset
- The last study drug administration date prior to the SAE
- Actions taken to treat the event (i.e. treatment medications, temporary discontinuation)
- Serious criteria
- The relationship of the event to the study drug or to the study procedure (e.g. the investigator's [or designee's] assessment of causality)
- A brief narrative of the SAE

Follow-up reports to already reported SAEs should contain any new information or query responses and must be documented on the SAE eCRF using the same process and timelines as for the initial SAE report.

9.3.4.9 24-Hour Emergency Contact

In a study-related medical emergency situation, when the assigned medical monitor cannot be reached, an on-call physician can be reached 24 hours per day, 7 days per week.

CCI	

9.3.4.10 Reporting of Suspected Unexpected Serious Adverse Reactions

A suspected unexpected serious adverse reaction (SUSAR) is an SAE experienced by a patient for which the nature or severity of which is not expected per the applicable product information (e.g. the Investigator's Brochure for an unauthorised investigational product or summary of product characteristics for an authorised product). The safety

information for A3907 is located in the reference safety information section of the current Investigator’s Brochure.

The sponsor and/or its designee are responsible for reporting SUSARs to regulatory authorities, central ethics committees, and investigators (or designees) within required timelines.

The investigator (or designee) is responsible for submitting required safety information to their local IRB or IEC per local regulations.

9.3.5 Laboratory Assessments

Clinical safety laboratory evaluations ([Table 2](#)) will be performed by a central laboratory. Samples will be collected for clinical laboratory evaluations at timepoints indicated in [Table 1](#). All samples will be processed and transported per instructions in the laboratory manual.

Table 2 Laboratory Parameters

Clinical Chemistry	Hematology	Urinalysis

 Albumin Alanine aminotransferase (ALT) Alkaline phosphatase (ALP) Aspartate aminotransferase (AST) Bilirubin – total and conjugated Blood urea nitrogen (BUN) Calcium Chloride Creatinine Creatine phosphokinase Gamma-glutamyl transferase (GGT) Lactate dehydrogenase Potassium Sodium Low-density lipoprotein cholesterol (LDL-C) 	Coagulation	
 Blood Glucose Ketones Leukocytes Nitrites pH Protein Oxalate
	
 Haematocrit Haemoglobin Platelet count Red blood cell count White blood cell count and differential (neutrophils, eosinophils, basophils, lymphocytes, and monocytes) 	
	
 Prothrombin time Activated partial thromboplastin time Thrombin time 	

Note: pharmacodynamic laboratory parameters are detailed in [Section 9.5](#).

The observed values will be recorded and assessed as “normal,” “abnormal not clinically significant,” or “abnormal clinically significant”.

For hepatic adverse events and/or hepatic decompensation, a PK sample should be collected as close to the onset of the event as possible.

Additional safety blood samples may be needed due to follow up of an abnormal value or analysis failure. The blood samples collected for safety laboratory analysis will be destroyed after the study has been completed.

9.3.6 Individual Patient Safety Monitoring

9.3.6.1 Liver Monitoring

Strategies to monitor markers of liver disease throughout the study are outlined below where the ULN will be based on central laboratory reference values. To make the distinction among the type of injury, and to make a causality assessment, the Roussel Uclaf Causality Assessment Method ([Appendix 2](#)) will be used.

For abnormalities classified as hepatic adverse events and/or hepatic decompensation, a PK sample should be collected as close to the onset of the event as possible.

If isolated transaminase elevations are observed, defined as:

Normal bilirubin AND absence of clinical hepatitis symptoms AND

- ALT or AST $\geq 5 \times$ ULN (if normal at baseline) OR
- ALT or AST $\geq 3 \times$ baseline (if abnormal at baseline) or > 500 U/L, whichever comes first

Then:

- a. Repeat liver profile (AST, ALT, bilirubin, and prothrombin time [PT] or INR) within 2 to 3 days
- b. Evaluate creatine phosphokinase (CPK) and lactate dehydrogenase (LDH)
- c. As needed (for example, persistent ALT/total bilirubin elevation or worsening of liver function), consider evaluation for alternative etiologies

Monitor the patient using the close observation guidelines found below.

If any ONE of the following criteria are met:

1. Transaminases (ALT or AST $\geq 3 \times$ baseline or 500 U/L, whichever comes first) AND bilirubin (total bilirubin $> 2 \times$ ULN) elevations
2. Transaminase elevations alone (ALT or AST $> 10 \times$ ULN or $5 \times$ baseline or absolute threshold of 800 U/L, whichever comes first) in presence of normal LDH and CPK
3. Total bilirubin increased, unrelated to hemolysis (elevated reticulocyte count) or established genetic diseases, such as Gilbert's syndrome

- a. Doubling if total bilirubin was < 3 mg/dL (equivalent to $51.3 \mu\text{mol/L}$) at baseline
OR
 - b. Increase by > 3 mg/dL (equivalent to $51.3 \mu\text{mol/L}$) if total bilirubin was ≥ 3 mg/dL (equivalent to $51.3 \mu\text{mol/L}$) at baseline
4. INR increase refractory to vitamin K administration
- a. Increase by > 1.5 if INR was normal at baseline OR
 - b. Increase by > 0.4 if INR was abnormal at baseline
5. Any increase in total bilirubin and transaminases if accompanied by EITHER a symptom of clinical hepatitis (e.g. vomiting, nausea, right upper quadrant pain) OR immunological reaction (rash or $> 5\%$ eosinophilia)

Then:

- a. Interrupt study medication
- b. Initiate drug-induced liver injury work-up for alternative etiologies
- c. Repeat liver profile (AST, ALT, total bilirubin, direct bilirubin) and PT or INR within 48 to 72 hours
- d. Monitor the patient using the close observation guidelines found below.

Close Observation

For patients requiring closer observation:

- Repeat liver enzyme and serum bilirubin tests two or three times weekly.
Frequency of re-testing can decrease to once a week or less if abnormalities stabilise or the study drug has been discontinued and the patient is asymptomatic
- Obtain a more detailed history of symptoms and prior or concurrent diseases
- Obtain a history of concomitant drug use (including non-prescription medications and herbal and dietary supplement preparations), alcohol use, recreational drug use, and special diets
- Consider ruling out alternate etiology including acute viral hepatitis types A, B, C, D, and E; autoimmune or alcohol-associated liver disease; non-alcoholic steatohepatitis (NASH); hypoxic/ischemic hepatopathy; and biliary tract disease
- Obtain a history of exposure to environmental chemical agents
- Obtain additional tests to evaluate liver function, as appropriate (e.g. INR, direct bilirubin)
- If the Roussel Uclaf Causality Assessment Method (RUCAM) scoring meets DILI criteria, the patient must be discontinued from the study drug.

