This is the first time A3907 will be administered to patients with PSC. Potential risks in the patient population are unknown. The potential risks associated with A3907 treatment will be mitigated by routine monitoring as noted in [Section 9.3](#). The study has been designed with a lead-in period to determine the exposure of A3907 in individual patients to ensure that exposure levels observed at the highest dose level in A3907-001 are not exceeded. Additionally, enrollment into Arm 2 will only begin after at least 3 patients in Arm 1 have completed 2 weeks of treatment at the lower dose and an SRC has reviewed safety and PK data ([Section 10.2.5](#)). For Arms 3 and 4, enrollment will only begin after at least 3 patients in Arm 2 have completed 2 weeks of treatment at the 30 mg dose QD dose, and an SRC has reviewed safety and PK data ([Section 10.2.5](#)). The SRC will also review safety data from this study on an ongoing basis and after the last patient reaches 12 weeks. Thus, exposure of patients in this study is justified by the anticipated benefits that may be afforded to the wider population of patients by continued development of A3907.

Benefit assessment

This study is designed to evaluate the safety, tolerability, PK, and PD of A3907 in patients with PSC. The dose selected is expected to reduce bile acid transport, leading to a decrease in serum bile acids, and positively influence liver enzymes and markers of liver fibrosis. It is not known whether patients participating in this study will benefit from the treatment. Due to the short duration of this study, any benefit observed is not expected to persist beyond the end of the study. However, the increased understanding of the effects of A3907 in this population may potentially result in new treatment options that would ultimately benefit patients with PSC.

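### Protocol 9.3.6.1: with total bilirubin above 1 and up to 2 x ULN, a newly detected, asymptomatic ALT/AST rise of 3 to under 5 x a raised baseline (and no more than 10 x ULN) meets neither liver action tier

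*Protocol*

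**What the plan says.** Protocol 9.3.6.1 defines two tiers.

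**Tier 1**, labelled as isolated transaminase elevation, begins "Normal bilirubin AND absence of clinical hepatitis symptoms AND" and then sets a size: at least 5 x ULN from a normal baseline, or at least 3 x baseline (or above 500 U/L) from an abnormal one. The response is a repeat profile in 2 to 3 days, CPK and LDH, and close observation, which includes: "Repeat liver enzyme and serum bilirubin tests two or three times weekly".

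**The interruption tier** stops drug and starts a liver-injury work-up if any one of five criteria is met:
1. An ALT/AST rise to at least 3 x baseline that comes with raised bilirubin. The text joins the two parts in the words "or 500 U/L, whichever comes first) AND bilirubin (total bilirubin", and the bilirubin limit it then gives is more than 2 x ULN.
2. An ALT/AST rise to 5 x baseline or above 10 x ULN, with one more limit and a condition: "or absolute threshold of 800 U/L, whichever comes first) in presence of normal LDH and CPK". A patient in whom either of those two enzymes is abnormal therefore cannot meet it.
3. A bilirubin criterion, worded "Total bilirubin increased, unrelated to hemolysis (elevated reticulocyte count) or established genetic diseases". It means a doubling from a baseline below 3 mg/dL, or a rise of more than 3 mg/dL from a higher one.
4. An INR increase that vitamin K does not correct.
5. A combined criterion, worded "Any increase in total bilirubin and transaminases if accompanied by EITHER a symptom of clinical hepatitis". Rash or eosinophilia above 5% serves in place of the symptom.

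SAP 9.2.1 counts patients by these five criteria only. Protocol 5.5 says of PSC patients "Potential risks in the patient population are unknown". It then points to Section 9.3 for the answer: "The potential risks associated with A3907 treatment will be mitigated by routine monitoring as noted in".

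**The concern.** Tier 1 ends where bilirubin leaves the normal range. The combined ALT/AST and bilirubin criterion starts only above 2 x ULN. Between those levels nothing in the section is triggered by a moderate ALT/AST rise alone. For the same newly found ALT, a timed retest is required at normal bilirubin, none is required in the band, and interruption is required above it. The plan gives no reason for that ordering.

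What is at stake is how soon a possible early liver signal is rechecked in the first study of this drug in PSC. The primary endpoint and its analysis are not affected.

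**Working it through.** The documents give no figure to reproduce here, so the check sets the rules side by side.

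**Inputs.** The thresholds are those of 9.3.6.1. Entry limits come from Section 7.2.2: ALT and AST up to 5 x ULN; total bilirubin below 1.5 x ULN in Arms 1-3 unless due to Gilbert's or hemolysis, with normal direct bilirubin. That bilirubin criterion does not apply to Arm 4. Visit days come from protocol Table 1. The documents give no ALT/AST ULN in U/L, so 40 U/L is assumed and 30 to 55 was tried. Normal bilirubin is read as total bilirubin at or below ULN, and 5 x baseline as at least 5 x.

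**ALT/AST limits.** Let b be baseline and a the on-treatment value, both in x ULN, with normal LDH and CPK.
- For b > 1, Tier 1 size means a ≥ 3b. Criterion 2 is not met while a < 5b and a ≤ 10.
- The gap is therefore 3b ≤ a < 5b with a ≤ 10. It exists only if 3b ≤ 10, so b ≤ 10/3 = 3.33.
- b = 1.5: 4.5 to under 7.5. b = 2: 6 to under 10. b = 3: 9 to 10. b = 3.34: 3b = 10.02, so criterion 2 is met and there is no gap.
- For b ≤ 1, Tier 1 size is a ≥ 5, which is already at least 5b. Criterion 2 is met and there is no gap.
- With ULN up to 50 U/L, 10 x ULN is at most 500 U/L, so the 500 and 800 U/L limits change nothing. At ULN 55, values of 501-550 U/L are also open for baselines of 3.3 to 5 x ULN.

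**Bilirubin limits.** The band is above 1 and up to 2 x ULN, and below twice baseline because of criterion 3. Baseline 0.5: none. Baseline 0.6: above 1 to under 1.2. Baseline 0.8: to under 1.6. Baseline 0.9: to under 1.8. Baseline above 1.0, or an exempt rise: up to 2.0.

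**Worked case (ULN 40 U/L).** ALT goes from 80 to 280 U/L (280/80 = 3.5 x baseline; 280/40 = 7 x ULN). Bilirubin goes from 0.9 to 1.4 x ULN (1.4/0.9 = 1.56 x baseline). LDH and CPK are normal, INR is unchanged, and there are no symptoms, rash or eosinophilia.

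| Rule | Needs | Patient | Met? |
|---|---|---|---|
| Tier 1 | bilirubin ≤ 1 x ULN | 1.4 | No |
| Criterion 1 | bilirubin > 2 x ULN | 1.4 | No |
| Criterion 2 | ALT > 400 (10 x ULN), 400 (5 x baseline) or 800 U/L | 280 | No |
| Criterion 3 | bilirubin 1.8 x ULN (doubling) | 1.4 | No |
| Criteria 4, 5 | INR rise; symptom, rash or eosinophilia | none | No |

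For this patient the gap runs from ALT 240 to 399 U/L and bilirubin 1.01 to 1.79 x ULN. At bilirubin 1.0 the same ALT is Tier 1. A patient with stable bilirubin of 1.3 x ULN and the same ALT rise also meets neither tier.

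**Abnormal LDH or CPK.** Criterion 2 cannot be met, so any Tier 1-size rise in the band is uncovered, including one from a normal baseline (from 5 x ULN, or 200 U/L).

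**Symptomatic rise without a bilirubin increase.** ALT 80 to 280, bilirubin unchanged at 0.9, nausea. Tier 1 fails on symptoms, criterion 5 fails because bilirubin has not risen, and criterion 2 fails as above. Arm 4 may enter with nausea (inclusion 14).

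**Retest interval.** Chemistry is drawn on Days 14, 28, 42, 70, 98 and 112. Intervals are 14 days to Day 42 (10-18 with the ±2-day windows), 28 days from Day 42 to Day 98 (24-32), and 14 days to Day 112. Close observation at two or three tests a week gives 4-6 tests in 14 days or 8-12 in 28 days, fewer once values stabilise.

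**The case against.** The best reply is that the pattern is a narrow conjunction and that other safeguards exist. Investigators must judge laboratory results for clinical significance (9.3.4.3), extra samples may be taken (9.3.5), and dosing can be stopped for a related AE (7.2.4.1). The study halts for one related SAE or two related severe AEs (7.2.4.3). RUCAM is to be used, and a score meeting the liver-injury criteria requires discontinuation. The SRC meets periodically, and Section 5.5 also relies on the PK lead-in and staggered enrolment. No enzyme elevation was seen in the first-in-human or 13-week dog studies. Normal direct bilirubin at entry limits raised total bilirubin in Arms 1-3, and exclusion 14c lists jaundice, though inclusion 14 allows increasing jaundice in Arm 4.

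All of that stands and keeps the point moderate. It does not close the gap: none of these provisions sets an ALT level or retest deadline for this pattern.

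Three stronger readings are tempting and not supported.
- A reader might infer that monitoring is withdrawn as bilirubin climbs. It is not. Nothing ends close observation when bilirubin leaves normal, and retesting may slow only once abnormalities stabilise, or the drug is stopped and the patient is asymptomatic. The gap concerns rises first detected in the band.
- A reader might set 8-12 tests against one scheduled chemistry throughout. That contrast holds only from Day 42 to Day 98.
- A reader might take the word alone in criterion 2 to exclude any raised bilirubin, leaving no upper ALT limit even with normal LDH and CPK. That is a strained reading of a safety rule, and this finding does not rest on it.

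Timing is also a fair objection. The planned period is 2022-2025 and the SAP cites a March 2025 drug dictionary, so an amendment may come late. The documents do not say whether dosing has finished.

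**Conclusion.** The gap is real and follows from the written rules. With normal LDH and CPK and a ULN up to 50 U/L, it covers baselines above 1 and up to about 3.3 x ULN, rises of 3 to under 5 x baseline and no more than 10 x ULN, and non-doubled or exempt bilirubin above 1 and up to 2 x ULN, without symptoms, rash, eosinophilia or an INR trigger. Abnormal LDH or CPK extends it to any Tier 1-size rise in the band. A symptomatic Tier 1-size rise below criterion 2, without a bilirubin increase, is a second gap.

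The consequence is a missing mandated retest for up to 14 or 28 days by schedule, not an absence of oversight. How many of about 24 patients would be affected cannot be derived. Gap patients are outside the SAP 9.2.1 count but still appear in its eDISH plots, the liver test tables and the laboratory listings.

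**What to change.** In Tier 1, replace the bilirubin and symptom conditions with *not meeting any interruption criterion below*, and change the word isolated in its heading to match. Every Tier 1-size rise then either meets an interruption criterion or falls into Tier 1, so both gaps close. Widening Tier 1 only to bilirubin of 2 x ULN would leave the symptomatic gap. Interruption thresholds stay unchanged; for a symptomatic patient brought into Tier 1 the change mandates retesting, and stopping drug remains the investigator's decision.

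Optionally, add a separate row to the SAP 9.2.1 count for patients meeting the widened Tier 1.

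The cost is a protocol amendment with ethics and authority approval (Section 13.1), since safety triggers change, plus at most 4-6 extra panels per affected patient in a 14-day interval or 8-12 in a 28-day one. If 1 to 3 patients are assumed, that is 8-36 panels over 28 days. If dosing has ended, the SAP row is still useful and the wording should be corrected before reuse.
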